### **8.3.5 Reporting Serious Adverse Events on the SAE Report Form**

All SAEs must be reported immediately to the Sponsor and/or its designated safety management vendor.

To report an SAE, the investigator must fax an SAE Report Form to Sponsor's designated safety management vendor within 24 hours of becoming aware of the serious event. In case of emergency or doubt, the Investigator shall call Sponsor's Medical Monitor for guidance. Follow-up reports must be submitted in a timely manner as additional information becomes available.

Full details of the SAE should also be recorded on the medical records and onto the eCRF. The following minimum information is required:

- Subject number, sex and age
- The date of report
- A description of the SAE (event, seriousness of the event)
- Causal relationship to the study drug

Follow-up information for the event should be sent promptly (within seven days) as necessary.

For each SAE observed, the investigator should obtain all of the information available about the event, including (but not limited to): hospital discharge diagnoses, hospital discharge note, death certificate, appropriate laboratory findings (including autopsies and biopsy results), and clinical examinations (including radiological examinations and clinical consultations).

### **8.3.5.1 Reporting Serious Adverse Events to the Institutional Review Board / Independent Ethics Committee**

The investigator is responsible for notifying his/her Institutional Review Board (IRB) or Ethics Committee (EC) of SAEs in accordance with local regulations. Sponsor, or its safety representative, will provide to the investigator a copy of any expedited safety reports that it intends to file with a regulatory authority.

### **8.3.5.2 Deaths**

For any death occurring during the subject's study participation, regardless of attribution, the investigator will report the death immediately to the Sponsor's Medical Monitor and their designated safety management vendor.

The investigator should notify Sponsor and their designated safety management vendor of any death or other SAE occurring after a subject has discontinued or terminated study participation that may reasonably be related to the study.

The investigator must submit the SAE Report Form and complete the appropriate eCRF for the event that led to the subject's death.

When reporting a death, the event or condition that caused or contributed to the fatal outcome should be recorded as the primary event term on the SAE Report Form.

### **8.3.6 Pregnancies: Reporting and Follow-up of Subjects**

A pregnancy in a female subject must be confirmed by positive serum  $\beta$ -hCG test. If  $\beta$ -hCG test is found positive in a female subject of childbearing potential, study drug should be placed on hold temporarily until pregnancy is ruled out via a repeat test  $\geq 3$  days. If a female subject becomes pregnant while the subject is receiving study treatment or within 12 weeks after the last dose of study treatment, a Pregnancy Report Form must be completed and submitted to Sponsor (by way of its designated safety management vendor) within 24 hours of the investigator learning of the pregnancy. The investigator should report the information to the sponsor on the designated forms. If applicable, a pregnant subject is immediately withdrawn from receiving study treatment. The investigator must follow the pregnancy to completion to ascertain both its outcome and whether any AEs occurred.

Pregnancy itself is not an AE unless there is a suspicion that the investigational product under study may have interfered with the effectiveness of a contraceptive medication. Pregnancies are followed up to outcome even if the subject was discontinued from the study. The outcome of the pregnancy must be reported by the investigator, which should be sent to the Sponsor and/or its designated safety management vendor within 24 hours of the investigator learning of the outcome. Congenital abnormalities/birth defects and spontaneous miscarriages should be reported and handled as SAEs. Elective abortions without complications should not be handled as AEs.

Pregnancy of the subject's partners is not considered to be an AE. However, the outcome of all pregnancies (spontaneous miscarriage, elective termination, ectopic pregnancy, normal birth or congenital abnormality) should if possible be followed up and documented as described. To capture information about a pregnancy from the partner of a male subject, the male subject's partner consent must be obtained to collect information related to the pregnancy and outcome

(should be handled on a case by case basis with IRB/IEC approval); the male patient should not be asked to provide this information.

### **8.3.7 Abnormal Laboratory Findings**

Laboratory values will be collected throughout the study to assess for safety. The investigator must review and assess all laboratory results in a timely manner, and determine whether the abnormal laboratory values, if any, are clinically significant (CS) or not clinically significant (NCS), and whether there are associated signs and symptoms.

An abnormal laboratory finding should be defined as an AE only if the abnormality meets one of the following criteria:

- Induces clinical signs or symptoms
- Requires active intervention
- Requires interruption or discontinuation of study medication
- In the opinion of the investigator, the abnormality is clinically meaningful and significantly different from baseline

If the abnormal laboratory finding is accompanied by signs or symptoms, report the signs and symptoms as the AE in lieu of the abnormal laboratory value. If a diagnosis is available, report the diagnosis.

A decrease in Hb value without any significant clinical symptoms should not be reported as an adverse event. In this case, worsening of anemia as evidenced by drop in Hb value may be considered as lack of efficacy as opposed to AE as the subject fails to respond adequately to study drug.

### **8.3.8 Disease Progression**

Disease progression can be considered as a worsening of a subject's condition attributable to the disease for which the investigational product is being studied. It may be an increase in the severity of the disease under study and/or increases in the symptoms of the disease. Gradual worsening of ESRD should be considered disease progression and should not be reported as an AE during the study.

## 9 STATISTICAL CONSIDERATIONS

### 9.1 Sample Size Determination

At least 600 subjects will be enrolled in this study. During the course of this study, which is being conducted in parallel with other Phase 3 studies, up to 1200 subjects may be enrolled for safety evaluation of roxadustat in comparison to epoetin alfa including adjudicated and prespecified safety events of interest (ie, all-cause death, MI, stroke, congestive heart failure requiring hospitalization, unstable angina requiring hospitalization, DVT, pulmonary embolism, vascular access thrombosis, and hypertensive emergency). The final number of patients to be enrolled will be based on the enrollment rate of other studies within the same indication, in order to optimize stopping these studies at comparable time frame

With at least 600 subjects, the study will provide at least 99% power to demonstrate statistical noninferiority of roxadustat versus ESA in the primary endpoint for US (FDA) submission (ie, specifically, Hb change from baseline to the average level during the evaluation period defined as Week 28 until Week 52).

The study will provide at least 99% power to demonstrate statistical noninferiority of roxadustat versus ESA in the primary endpoint outside of the United States (ie, specifically, Hb change from BL in the averaged Hb over Weeks 28 to 36).

This assumes a difference (roxadustat minus ESA) of 0.30 g/dL, a noninferiority margin for this difference of 0.75 g/dL and a standard deviation of 1.25 g/dL.

### 9.2 Randomization

Randomization will be stratified by the following three factors:

- Mean qualifying screening hemoglobin ( $\leq 10.5$  vs.  $> 10.5$  g/dL)
- History of CV, cerebrovascular, or thromboembolic diseases (yes vs. no)
- Mean prescribed weekly epoetin alfa dose (or, equivalent epoetin dose for nonpoetin subjects) in the 4 weeks prior to randomization ( $\leq 150$  vs.  $> 150$  IU/kg/week)
- Geographical region (US vs. Ex-US regions)

### 9.3 Analysis Populations

For US regulatory submission, efficacy and safety analyses will be based on all subjects stratified by the protocol amendments, on subjects enrolled during the original protocol but before the amendment 1, and on subjects enrolled after the amendments separately.

For EU regulatory submission, efficacy and safety analyses will be based on subjects enrolled during the original protocol before the amendments, as the subjects enrolled after the amendments may be considered as a sub-study for EU regulatory purpose.

The following analysis sets are defined and will be used for the statistical analysis.

#### 9.3.1 Intent to Treat Population (ITT)

The ITT population consists of all randomized subjects.

### **9.3.2 Full Analysis Set (FAS)**

The FAS consists of all randomized subjects who receive at least one dose of study drug and have at least one postdose Hb assessment. If treatment received differs from the randomized treatment, the randomized treatment arm will be used.

### **9.3.3 Per-Protocol Set (PPS)**

The PPS consists of all randomized subjects who received at least 8 weeks of study treatment, have at least one postdose Hb assessment and are without major protocol violations.

### **9.3.4 Safety Analysis Set (SAF)**

The SAF will consist of all randomized subjects who received at least one dose of study medication. If treatment received for the duration of the study differs from the randomized treatment, the actual treatment arm will be used.

## **9.4 Statistical Analysis**

Safety and efficacy data will be summarized and presented by treatment group in summary tables. Descriptive statistics including number of subjects (N), means, standard deviations, medians, and minimum and maximum values will be presented for continuous variables. Counts and percentages will be presented for categorical variables. For efficacy endpoints, the standard error and 95% confidence intervals (CI) will be presented as part of the descriptive summaries.

### **9.4.1 Subject Enrollment and Disposition**

The number of randomized subjects (ITT), treated subjects, FAS and PPS subjects and subjects who discontinued along with the reason for early termination will be summarized by treatment group and overall.

### **9.4.2 Demographics and Baseline Characteristics**

Demographics (age, race, sex), BL characteristics including stratification factors, and subject disease characteristics will be summarized.

Descriptive statistics will be calculated for continuous variables (eg, age, weight, BL Hb, body mass index) and frequency counts and percentages will be tabulated for categorical variables (eg, sex, race, Hb category, iron status, and history of CV disease or cerebrovascular disease) by treatment group and overall.

### **9.4.3 Efficacy Analyses**

Efficacy analysis for superiority will be conducted on the ITT population for US (FDA) submission and on FAS population for EU regulatory submission.

Efficacy analysis for non-inferiority will be conducted on the ITT population for US (FDA) submission and on the PPS for EU regulatory submission.

Hb results obtained from the central laboratory will be used for all efficacy analyses. Baseline Hb value for efficacy analysis is defined as the mean of four central laboratory Hb values, three of the latest screening Hb values plus the pre-dose Hb value collected on Day 1 for subjects who enrolled under original protocol and Amendment 1. Subjects enrolled under Amendment 2, baseline Hb value for efficacy analysis is defined as the mean of three central laboratory Hb values, two of the latest screening Hb values plus the pre-dose Hb value collected on Day 1.

In subjects with missing Day 1 Hb value, the mean of three (two, for Amendment 2) latest screening laboratory Hb values will be considered as BL Hb value.

#### 9.4.3.1 Primary Efficacy Analysis

The primary efficacy endpoint for the US (FDA) submission is defined as the Hb change from baseline to the average level during the evaluation period defined as Week 28 until Week 52. The analysis will be based on the all ITT population, Sensitivity analyses will be performed on ITT Population enrolled under the original protocol, and the ITT population enrolled under amended protocols, separately.

The primary hypothesis to be tested for the primary efficacy analysis is:

$H_0$ : Hb mean change from baseline to the average level from Week 28-to Week 52 in the roxadustat group  $\leq$  Hb mean change from baseline in the epoetin alfa group minus 0.75 g/dL

Versus:

$H_1$ : Hb change from baseline to the average level of Week 28 to Week 52 in the roxadustat group  $>$  Hb mean change from baseline in the epoetin alfa group minus 0.75 g/dL

A Multiple Imputation Analysis of Covariance (MI-ANCOVA) model will be used. The model will contain terms for baseline Hb measurement as covariate, treatment arm, and randomization stratification factors except Screening Hb values ( $\leq 10.5$  g/dL vs.  $> 10.5$  g/dL) as fixed effects. Detailed analysis of the primary endpoint will be outlined in the SAP.

In addition, as a sensitivity analysis, the primary efficacy endpoint will be analyzed using the analysis of MMRM model. The MMRM model will contain terms for baseline Hb measurement as covariate, treatment arm, visit, visit by treatment arm, and randomization stratification factors except Screening Hb values ( $\leq 10.5$  g/dL vs.  $> 10.5$  g/dL) as fixed effect. The primary efficacy analysis (for both, US [FDA] and EU regulatory submissions) will be based on the estimated difference between the two treatments overall mean effects throughout the evaluation period based on the primary analysis models.

Due to the large amount of visits to include in the MMRM model, the unstructured covariance pattern model will be tested against the less parameterized heterogeneous Toeplitz structure using the likelihood ratio test for nested models. If the algorithm for unstructured covariance pattern does not converge or the likelihood ratio test is not statistically significant then heterogeneous Toeplitz structure will be used. If this second model does not converge either then the (homogeneous) Toeplitz structure will be tried and finally compound symmetry as a covariance structure to achieve convergence.

Pattern Mixture models will be used as additional sensitivity analyses. The details will be described in the SAP.

Hb values under the influence of a rescue therapy will not be censored in the primary analysis.

The null hypothesis will be rejected if the two-sided 95% CI for the difference between the two least squares means of the roxadustat group and the epoetin alfa group throughout the evaluation lies entirely above  $-0.75$  g/dL

The primary efficacy endpoint for EU regulatory submission is defined as the Hb change from BL to the average Hb of Weeks 28 to 36, without having received rescue therapy within 6 weeks prior to and during this 8-week evaluation period and will be based on the PPS population enrolled under original protocol only. This primary efficacy analysis will be based on the estimated difference between the two treatments overall mean effects throughout the evaluation period based on the same MMRM model as the sensitivity analysis of primary efficacy endpoint for US regulatory submission.

For subjects who discontinued the study prior to Week 28, the last Hb value will be used in the assessment of the primary endpoint.

The primary hypothesis to be tested for the primary efficacy analysis is:

H0: Hb mean change from BL to the average of Weeks 28 to 36 in the roxadustat group  $\leq$  Hb mean change from BL in the epoetin alfa group minus 0.75 g/dL

Versus:

H1: Hb change from BL to the average of Weeks 28 to 36 in the roxadustat group  $>$  Hb mean change from BL in the epoetin alfa group minus 0.75 g/dL

For subjects who require rescue therapy, the Hb value after to the initiation of the rescue therapy will be set to missing up to 6 weeks from the last date of the rescue therapy. This null hypothesis will be rejected if the two-sided 95% CI for the difference between the two treatment groups using MMRM model lies entirely above  $-0.75$  g/dL.

The analysis will be repeated using the FAS as a sensitivity analysis.

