11.1 Analyses of Primary Endpoint

11.1.1 Primary Endpoint and Hypothesis

11.1.1.1 U.S. Submission

The primary efficacy endpoint for the US (FDA) submission is defined as the hemoglobin change from baseline to the average level during the evaluation period defined as Week 28 until Week 52.

The primary hypothesis to be tested for the primary efficacy analysis for US (FDA) submission is:

H_0 : Hemoglobin mean change from baseline to the average level from Week 28 to Week 52 in the roxadustat group \leq hemoglobin mean change from baseline in the epoetin alfa group minus 0.75 g/dL

Versus:

H_1 : Hemoglobin change from baseline to the average level of Week 28 to Week 52 in the roxadustat group $>$ hemoglobin mean change from baseline in the epoetin alfa group minus 0.75 g/dL

A Multiple Imputation (MI) analysis of covariance (ANCOVA) model will be used. The model will contain terms for treatment group, baseline Hb measurement, and stratification factors except mean qualifying screening hemoglobin (≤ 10.5 vs. >10.5 g/dL). The primary efficacy analysis will be based on the estimated difference between the two treatments overall mean effects throughout the evaluation period based on the pooled ANCOVA model.

This null hypothesis will be rejected if the two-sided 95% CI for the difference between the two treatment groups using MI ANCOVA model lies entirely above -0.75 g/dL. Hemoglobin values under the influence of a rescue therapy will not be censored in this analysis.

The below stratification factors will be used in efficacy analyses.

- Mean qualifying screening hemoglobin (≤ 10.5 vs. >10.5 g/dL) for other than Hb related endpoints
- History of CV, cerebrovascular, or thromboembolic diseases (yes vs. no)
- Mean prescribed weekly epoetin alfa dose (or, equivalent epoetin dose for nonepoetin subjects) in the 4 weeks prior to randomization (≤ 150 vs. > 150 IU/kg/week)
- Incident dialysis within ≤ 4 months vs. > 4 months of starting dialysis when randomized.

The following steps will be used to conduct the primary analysis of the primary endpoints for both regions:

1. Generate 200 datasets, using seed 162345 for U.S. and 347631 for Ex-U.S., where only intermittent missing hemoglobin data will be imputed for each treatment relying on non-missing data from all subjects within each treatment group using the Monte Carlo Markov Chain, MCMC) imputation model and the available non missing hemoglobin for each scheduled Week by treatment group.

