11.1.1.2 EU Regulatory Submission

The primary efficacy endpoint for Ex-U.S. submission is defined as the hemoglobin change from baseline to the average hemoglobin of Weeks 28 to 36, without having received rescue therapy within 6 weeks prior to and during this 8-week evaluation period and will be based on the PPS population based on patients enrolled during the original protocol before the amendment 1. This primary efficacy analysis will be based on the estimated difference between the two treatments overall mean effects throughout the evaluation period based on the MMRM model described below.

The primary hypothesis to be tested for the primary efficacy analysis for Ex-US submission is:

H_0 : Hemoglobin mean change from baseline to the average of week 28 to week 36 in the Roxadustat group
 \leq Hemoglobin mean change from baseline in the Epoetin alfa group minus 0.75 g/dL

Versus

H_1 : Hemoglobin change from baseline to the average of week 28 to week 36 in the roxadustat group
 $>$ Hemoglobin mean change from baseline in the Epoetin alfa group minus 0.75 g/dL

Rescue therapy for all subjects is defined as ESA rescue or RBC transfusion. For subjects who require rescue therapy, the hemoglobin value after the initiation of the rescue therapy will be set to missing up to 6 weeks (or 8 weeks if during the evaluation period) from the last date of the rescue therapy.

The primary endpoint for EU Regulatory. will be analyzed using MMRM using baseline value as covariate and treatment group, visit (up to Week 52), interaction of treatment group

and visit, and stratification factors except mean qualifying screening hemoglobin (≤ 10.5 vs. >10.5 g/dL) as fixed effects.

Due to the large amount of visits (up to Week 52) to be included in the model, the unstructured covariance pattern model will be applied first. If the algorithm for unstructured covariance pattern does not converge then the heterogeneous Toeplitz structure will be used. If this second model does not converge either then the (homogeneous) Toeplitz structure will be tried and finally compound symmetry as a covariance structure to achieve convergence.

The estimates for difference of change in Hb averaged over Weeks 28 to 36 between the two treatment groups will be generated from an estimate statement from Visit Week 28 to 36.

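### The protocol's EU (Ex-US) primary analysis uses the last Hb of subjects who left before Week 28, but the MMRM in the protocol and SAP has no carry-forward step and the SAP does not flag the difference

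*Protocol*

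**What the plan says.** Protocol 9.4.3.1 defines the EU primary endpoint on the per-protocol set (PPS) of subjects enrolled under the original protocol. The analysis is "based on the same MMRM model as the sensitivity analysis of primary efficacy endpoint for US regulatory submission". Of that model the section says: "The MMRM model will contain terms for baseline Hb measurement as covariate, treatment arm, visit, visit by treatment arm, and randomization stratification factors". Non-inferiority is concluded if the two-sided 95% CI "for the difference between the two treatment groups using MMRM model lies entirely above" −0.75 g/dL.

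Between the EU endpoint definition and the EU hypotheses stands this sentence: "For subjects who discontinued the study prior to Week 28, the last Hb value will be used in the assessment of the primary endpoint". Its position ties it to the EU test. A separate rule in the same part sets Hb to missing after rescue therapy.

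SAP 11.1.1.2 has no counterpart to the sentence. It says: "The primary endpoint for EU Regulatory. will be analyzed using MMRM using baseline value as covariate", with visits up to Week 52, and the Weeks 28–36 difference "will be generated from an estimate statement from Visit Week 28 to 36". The SAP's one carry-forward method for Hb is the last-mean-carried-forward pattern-mixture model in 11.1.2.2.3, which is a sensitivity analysis.

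SAP 11.1.1.1, under the US heading, introduces its multiple-imputation ANCOVA with: "The following steps will be used to conduct the primary analysis of the primary endpoints for both regions". It also gives an Ex-US random seed.

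**The concern.** An MMRM as specified uses the visits that were observed and leaves a leaver's later visits missing, to be handled through the likelihood. The protocol sentence instead supplies a single value for the same subject. The two give different estimates and different confidence intervals for the confirmatory test against −0.75 g/dL.

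The affected subjects are not a null set. The PPS asks for at least 8 weeks of treatment (protocol 9.3.3, SAP 5.2.3), so someone who leaves between Week 8 and Week 28 can be in it. The sentence does not say which visits receive the value, whether an Hb taken after study drug stopped can be the last one, or how the rule works with Hb set to missing after rescue.

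With the SAP's multiple-imputation text added, three treatments of early leavers are on paper for one primary test in an open-label trial.

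**Working it through.** **1. The texts side by side**

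| Place | Weeks 28–36 Hb of a subject who left before Week 28 |
|---|---|
| Protocol 9.4.3.1, EU sentence | Last Hb value used |
| Protocol 9.4.3.1, MMRM terms | No fill-in step |
| SAP 11.1.1.2 | No fill-in step; contrast taken from the MMRM |
| SAP 11.1.1.1, steps for both regions | Multiply imputed |

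**2. The plan's own figure.** Inputs from SAP 5.1 and the protocol synopsis: difference −0.30, margin 0.75, SD 1.25, at least 600 subjects at 1:1, so 300 per arm. The test level is two-sided 0.05.

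- SE = 1.25 × √(2/300) = 0.102
- Power = Φ((0.75 − 0.30)/0.102 − 1.96) = 99.28%
- Sample size needed for 99% power: 284 per arm

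The stated power of at least 99% is reproduced. It uses no dropout or carry-forward input, so the disputed sentence does not change it.

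**3. Effect on the standard error (illustration).** Let f be the share of early leavers. If carried values have the same variance as observed ones and count as data, while the leavers truly add no information, the reported SE is √(1 − f) times the correct one.

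- f = 0.10: √0.90 = 0.95
- f = 0.20: √0.80 = 0.89
- f = 0.30: √0.70 = 0.84

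Under equal variance this is the largest understatement, because an MMRM recovers some information from earlier visits. If carried values are more variable, the SE need not shrink this much.

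At the design assumptions, with an estimate of −0.30:

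- Lower limit with the nominal SE: −0.30 − 1.96 × 0.102 = −0.50
- Lower limit with the SE corrected for f = 0.30: −0.30 − 1.96 × (0.102/0.84) = −0.54

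Both are above −0.75. If leavers added nothing, power would be 98.7%, 97.6% and 95.8% at 10%, 20% and 30% loss.

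The original-protocol PPS may be smaller than 300 per arm; its size is not given. With f = 0.30, the corrected lower limit stays above −0.75 if n ≥ 2 × (1.96 × 1.25/0.45)² / 0.70, which is about 85 per arm.

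**4. Effect on the estimate (illustration).** Let d be the share leaving before Week 28 and g the last Hb change minus the change expected at Weeks 28–36, for roxadustat (T) and epoetin (C). The shift in the difference is d_T·g_T − d_C·g_C. The power column uses 300 per arm and −0.30 plus the shift.

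| d_T, d_C | g_T, g_C (g/dL) | Shift (g/dL) | Power |
|---|---|---|---|
| 20%, 20% | −0.5, −0.5 | 0 | 99.3% |
| 20%, 20% | −0.5, 0 | −0.10 | 92.9% |
| 30%, 15% | −0.5, 0 | −0.15 | 83.6% |
| 30%, 15% | +0.5, −0.5 | +0.225 | above 99.9% |

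The cases computed ran from −0.15 to +0.225 g/dL. The values of d and g are assumptions; neither document gives them.

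**The case against.** The strongest reply is that this is leftover wording with no practical effect. The protocol's summary of changes for Amendment 2 says that LOCF was taken out of the MMRM models. Protocol 9.6 leaves analysis details to the SAP, and the SAP's primary analysis contains no single-value carry-forward. That explanation is plausible. But the sentence is in the current text of 9.4.3.1, and the same 9.6 asks that significant changes be highlighted in the SAP. This one is not.

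A reader might infer that the protocol states two incompatible primary analyses. The documents do not support that: an MMRM can be fitted to filled data, and the section can be read as one model with an added data rule. What conflicts is the handling of the same subject's missing outcome.

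The affected group may also be small. The sentence concerns subjects who discontinued the study, which protocol 5.3 separates from stopping study drug. The PPS also drops subjects with under 8 weeks of treatment, compliance below 75% or other major deviations (SAP 5.2.5). This limits the likely size and is a good reason not to attach a firm number. It does not remove the inconsistency.

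**Conclusion.** The point holds as a real inconsistency in the stated confirmatory analysis. Followed literally, the sentence puts single imputation, treated as observed data, into the EU (Ex-US) non-inferiority test. The SAP omits it without saying so.

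A reader might go further and infer that the rule biases the trial towards non-inferiority or could overturn its result. The documents do not support that. The shift is zero when both arms share the same dropout share and gap, and otherwise can go in either direction. The SE factor of about 0.95–0.84 rests on an assumed 10–30% of early leavers and on equal variance. At the planned difference and SD, with 300 per arm, that understatement alone leaves the lower limit well clear of the margin. The reason to act is that the primary analysis should be fixed and single in an open-label trial; a wrong conclusion has not been shown to be likely.

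**What to change.** - **Protocol 9.4.3.1:** delete the sentence, or label it a sensitivity analysis and define the last value and the visits it fills. If no further amendment is planned, record the departure in the SAP, as protocol 9.6 provides.
- **SAP 11.1.1.2:** state that subjects who leave before Week 28 contribute only their observed Hb, excluding values set to missing for rescue, and that no single imputation is applied in the MMRM.
- **SAP 11.1.1.1:** reconcile the statement that the multiple-imputation ANCOVA steps are primary for both regions, so that one Ex-US primary analysis remains. Deleting the protocol sentence alone would leave this open.

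The cost is a few sentences. No sample size or power figure changes. A protocol change needs IRB/IEC approval before it is implemented (protocol 12.2); the SAP route is cheaper and enough to settle the analysis, provided that the departure is stated openly and before the data are analysed.
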